- To determine whether patients exhibit a change in vitreous haze, assessed clinically by the NEI and Davis scales at 6 months
- To determine whether patients exhibit a change in vitreous haze, assessed by the photographic grading of haze by the NEI and Davis scales at 6 months.
- To determine the proportion of patients discontinuing due to intolerability at six months.
- To determine the rate of adverse events experienced at six months.
- To determine the proportion of patients discontinuing due to serious adverse events at six months.
- To determine whether patients exhibit a change in quality of life at six months.
- Tabulate the occurrence of dose reduction used in immunosuppressive treatment (see Manual of Operations Section 3.1 for dose reduction guidelines).
- To determine efficacy of treatment in Vogt-Koyanagi-Harada (VKH) patients at six months.
- To determine the proportion of patients beginning with at least 2+ inflammation in anterior chamber cells and experience at least a 2-step reduction (i.e. decreasing from 2+ to 0.5+; 3+ to 1+; 4+ to 2+).
- To determine the proportion of patients beginning with at least 2+ inflammation in vitreous haze and experience at least a 2-step reduction (i.e. decreasing from 2+ to 0.5+; 3+ to 1+; 4+ to 2+0).

- To evaluate a difference in treatment success controlling for vasculitis at baseline, assessed at six months.
- To explore the use of a dynamic process model (such as a Hidden Markov model) to assess differences in control of inflammation.
- VKH) patients at six months.
 - Proportion of patients who started with at least 1+ inflammation levels in anterior chamber cells who achieve a decrease to 0 level of inflammation in anterior chamber cells.
 - Proportion of patients who started with at least 1+ inflammation levels in vitreous haze who achieve a decrease to 0 level of inflammation in vitreous haze.

All the above analyses will be examined at the end of Phase I (6-12 months), in addition to the following:

- To determine whether patients exhibit a difference in the probability of controlling inflammation with complete discontinuation of steroids at twelve months in Phase I.

2.3.2 Specific Aim 2

Primary Objective. The primary objective of this aim is to evaluate the clinical efficacy of switching agents as rescue therapy after initial treatment failure.

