categories: anterior/intermediate or intermediate only, and posterior/panuveitis). Anatomical location by history is considered the prespecified analysis; anatomical location at enrollment will supplement this finding.

We propose to proceed as follows. We propose to begin with Equation (1), adding terms $\beta_3 X_i^3 + \beta_{13} X_i^1 X_i^3$ for anatomic location and for treatment-location interaction. We wish to test the hypothesis that $\beta_{13} = 0$, i.e. that there is a difference in treatment efficacy between the anatomic locations, controlling for country. Alternative models will be fit in which the country, site, and treatment x country terms are omitted.

We will also report relative risks in each substratum, using relative risk regression.

Additional analyses will add gender and age to the predictors. The entire analysis will be repeated for each gender, and separately for each country (US and India) and anatomic location.

Planned Secondary Analyses.

Each of the following secondary analyses is designed to test the hypothesis that treatment assignment affects a given outcome, after controlling for selected covariates. All analyses will be repeated without controlling for covariates (i.e., using treatment assignment as the only predictor). In all cases, appropriate regression diagnostics and/or goodness of fit tests will be performed (further details are given below). In addition, we will compute jackknife influence statistics in each analysis, to determine whether or not any single observation (eyes or patients, as appropriate) have an undue effect on the final conclusion. All models with site effects will be repeated omitting this effect, and again repeated including a treatment-site effect, and with country and/or treatment by country interactions (i.e., pooling within countries when appropriate). When reporting findings, care will be taken to distinguish the single prespecified test from supplemental tests (whether prespecified or unprespecified); exploratory analyses will always be labeled as such. All alpha levels are to be two-sided.

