11. *Alternative definitions for success.* Other definitions will be examined: (i) changing the algorithm for assigning values for unobservable uveitis examination fields (anterior cells, vitreous haze, retinal/choroidal lesions) so that any worsening of ability to assess the eye for any reason is scored a failure, or (ii) use of vitreous cells in the definition of uveitis.

12. *Change in vitreous haze* will be assessed using clustered polytomous logistic regression, using baseline vitreous haze as a covariate and follow-up time. Vitreous haze is an ordinal outcome variable. A random effect is needed because the two eyes of a given patient cannot be treated as statistically independent. Both the NEI and Davis scales will be analyzed, for both direct observations and photographic grading. Treatment assignment will be a covariate. Alternative methods will be examined, including a simple McNemar test in which we dichotomize vitreous haze assessments at baseline and at the final observation.

13. *Rate of adverse events* and the proportion of patients discontinuing due to adverse events will be tabulated by treatment assignment, age, and gender; confidence intervals will be reported.

14. *Treatment efficacy in VKH patients* will be assessed as a planned subgroup analysis. Note that anatomic location is also a planned subgroup analysis, as well as study site and study country (aggregating all sites within each country).

15. *Dose reduction* will be compared by arm using logistic regression based on treatment, and other covariates as needed.

16. If no difference is found for the primary outcome comparing treatment success between arms, we will assess whether methotrexate is non-inferior to mycophenolate mofetil, assuming a 10% non-inferiority margin. The non-inferiority margin of 10% is clinically meaningful and was based on investigator consensus. Methotrexate will be considered non-inferior to mycophenolate if the lower limit of the 95% CI for treatment success at 6 months is less than 10%. This analysis will be conducted because mycophenolate mofetil is much more expensive than methotrexate, so a determination that methotrexate is not inferior has clinical implications. We are interested in a one-sided comparison given the cost differential between methotrexate and mycophenolate mofetil.

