3.4 Sample Size Evaluation

3.4.1 Primary Calculation

The sample size for the trial will be 216 subjects, which we anticipate will provide approximately 80% power to detect a difference of 20% in the proportion of patients achieving control of inflammation at six months between the methotrexate and mycophenolate mofetil groups.

This sample size was determined based on the primary objective (superiority comparison of mycophenolate mofetil to methotrexate) and primary endpoint (treatment success). We assumed an effect size of 20%, as this was deemed to be clinically meaningful, and well within the distribution of the investigators' prior beliefs from published retrospective studies.

An approximate sample size is provided by the formula

$$2N = \frac{4(Z_{\alpha} + Z_{\beta})^2 \bar{p}(1-\bar{p})}{(p_c - p_i)^2} \quad (5)$$

(see Friedman et al. 2010), where α is the significance level (0.05, two sided), β is one minus the power (the desired power is 80%), p_c is in this case the probability of success in the methotrexate group (we estimate this at 0.4), p_i is the probability of success in the mycophenolate mofetil group (we estimate this at 0.6), and \bar{p} is $\frac{1}{2}(p_i+p_c)$. We assume 10% will be lost to follow-up in the first six months; details are given in the full proposal. This yields approximately 108 patients in each of the two groups, for a total of $2 \times 108 = 216$ subjects.

A power table is provided below as a sensitivity analysis (to show how the detectable effect size changes with varying success rates).

Success rate with Drug A	80% Power		90% Power	
	Detectable effect size	Success rate with Drug B	Detectable effect size	Success rate with Drug B
20%	18%	38%	21%	41%
30%	20%	50%	23%	53%
40%	20%	60%	23%	63%
50%	20%	70%	22%	72%
60%	19%	79%	21%	81%

Simulation confirms that this method yields adequate sample sizes for the logistic regression (results not shown).

Note that for the final analysis, the critical value will be adjusted slightly because of the interim analysis.

Sample size readjustment

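### The McNemar test offered as an alternative for vitreous haze measures change over time and contains no comparison of methotrexate with mycophenolate, so it cannot test the stated hypothesis.

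*Combined protocol and SAP*

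**What the plan says.** SAP section 3.2.2 introduces its list of planned secondary analyses with one common purpose: "Each of the following secondary analyses is designed to test the hypothesis that treatment assignment affects a given outcome". It adds that each analysis will be repeated with treatment assignment as the sole predictor.

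Item 12 covers change in vitreous haze. Its main method is a clustered polytomous logistic regression that adjusts for baseline haze. On treatment it says "Treatment assignment will be a covariate", and on the two eyes "A random effect is needed because the two eyes of a given patient cannot be treated as statistically independent". It then adds: "Alternative methods will be examined, including a simple McNemar test in which we dichotomize vitreous haze assessments at baseline and at the final observation".

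Item 12 does not say how treatment arm would enter the McNemar test, where haze would be cut, which visit counts as final, or whether the pairs are eyes or patients. The matching objective in SAP section 2.3.1 reads "To determine whether patients exhibit a change in vitreous haze, assessed clinically by the NEI and Davis scales at 6 months" and does not mention a difference between arms.

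**The concern.** McNemar's test compares the two kinds of discordant pair. With baseline and final haze as the pair, these are patients whose haze cleared and patients whose haze appeared. The null hypothesis is that the two are equally frequent. Treatment arm plays no part in it.

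There is good reason to expect haze to fall on either drug. Patients must have active inflammation at entry, which builds in regression to the mean (protocol 2.3.2). All begin on high-dose oral prednisone (protocol 3.2.1). The baseline examination may precede randomization by up to 14 days, during which steroids may already have reduced the inflammation (protocol 4.3). A small P-value would reflect these shared influences. Because the test sits in a list described as tests of treatment assignment, a reader could take that P-value as evidence about the drugs.

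**Working it through.** **Number of patients.** Item 12 has no sample size of its own, so the trial's is used: "The sample size for the trial will be 216 subjects". Equation (5) of SAP 3.4.1 with 0.4 versus 0.6, two-sided 0.05 and 80% power gives 2N = 4 × (1.960 + 0.842)² × 0.5 × 0.5 / 0.2² = 196.2, and 196.2 / 0.9 = 218.0 after 10% loss. The two-proportion formula with pooled variance under the null gives 97 per arm, and 97 / 0.9 = 107.8, rounded up to 108 per arm. The planned 216 is therefore reproduced, and about 2 × 97 = 194 patients are observed at six months.

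**What the test responds to.** Let h be the proportion with haze at baseline, r the proportion of those who resolve, and w the proportion of the rest who develop haze. The expected discordant counts are b = 194·h·r and c = 194·(1 − h)·w, and approximately z = (b − c)/√(b + c). The null hypothesis is h·r = (1 − h)·w. None of these quantities is a difference between arms.

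**Inputs that the documents do not give.** h was varied from 10% to 100%, r from 30% to 80% and w from 0 to 10%. All are assumptions. The summary below uses r of 40–60%, borrowing the planned success rates of 0.4 and 0.6 as a proxy. The cut is taken as 0.5+ or less versus 1+ or more, following the control criterion in protocol Table 2.

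**Simulation with equal drugs.** There were 4,000 trials per scenario with 97 patients per arm, one binary haze value per patient, and an exact two-sided McNemar test at 0.05. Selected rows:

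| h | r | w | b | c | z | McNemar rejects |
|---|---|---|---|---|---|---|
| 0.5 | 0.5 | 0.05 | 48.5 | 4.9 | 5.98 | 100% |
| 0.5 | 0.4 | 0.10 | 38.8 | 9.7 | 4.18 | 98.9% |
| 0.3 | 0.4 | 0.10 | 23.3 | 13.6 | 1.60 | 29.3% |
| 0.2 | 0.4 | 0.10 | 15.5 | 15.5 | 0 | 3.4% |
| 0.1 | 0.4 | 0.10 | 7.8 | 17.5 | −1.93 | 40.7% |
| 0.1 | 0.6 | 0 | 11.6 | 0 | 3.41 | 97.7% |

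In the fifth row the expected change is an increase in haze, still with equal drugs. Over r = 40–60% and w = 0–10%, rejection is 99–100% for h of at least 0.5, 29–100% for h = 0.3, and 3–100% for h = 0.1–0.2. In two scenarios where haze does not change over time (6,000 trials each), it is 3.5% and 3.7%. The result follows change over time, not the drug effect.

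**A between-arm test on the same data.** A Mantel-Haenszel comparison of final haze by arm, stratified by baseline haze, rejects in about 4–6% of trials in every equal-drug scenario. With a true difference in resolution (40% versus 60%, h = 0.5, w = 0.05; 6,000 trials) it rejects in 44%. McNemar rejects in about 100% there, and also in about 100% when both drugs resolve 40% or both 60% at the same h and w.

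**McNemar run separately in each arm.** With equal drugs, one arm is significant and the other is not in up to about 52% of trials over the full grid (the maximum is at h = 0.5, r = 0.3, w = 0.10). Comparing two within-arm P-values is not a test of the drugs.

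**If eyes are the pairs.** With 194 patients, two eyes each, no change over time and 40% of eyes discordant (assumed), treating eyes as independent gives 3.8% false rejection at zero latent inter-eye correlation and about 6–13% at correlations of 0.3–0.9 (assumed).

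**The case against.** The strongest defence is that the drug comparison already exists. The main item 12 model contains treatment assignment, baseline haze and a random effect for the two eyes. McNemar is only one of several alternatives to be examined, and section 3.2.2 undertakes to separate the prespecified test from supplemental ones and to label exploratory work. This stands, and it is why the point is minor. A reader might infer that the haze comparison as a whole is invalid or that the two arms are never compared on haze. The documents do not support that.

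A second defence is that the objective asks about change, which McNemar does address, so rejecting no change after haze has fallen is a correct rejection. That is true of the test taken alone. It does not reconcile the test with the purpose given for the list. The visual acuity objective is also worded as change, yet item 4 tests whether treatment assignment affects it. Item 9, headed as change in macular thickness, is tested through the treatment-arm coefficient. In this SAP a change outcome is compared by arm.

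A third defence concerns certainty. A reader might infer that the test is bound to be significant. Entry does not require haze: anterior chamber cells or retinal or choroidal activity suffice (protocol 2.3.2). With few haze cases at baseline and some new haze, rejection can be as low as about 3%. Nor can one say that the test ignores the pairing of eyes, because the unit is not stated.

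**Conclusion.** The point holds at low severity. As described, the McNemar test has no treatment contrast and cannot test the hypothesis set for the secondary analyses. This follows from the form of the test and needs no assumption.

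How often it would mislead does rest on assumptions. With equal drugs, significance is near certain if about half or more of patients have haze of 1+ or more at baseline, and it can fall anywhere from 3% to 100% if only 10–20% do. Running the test by arm does not repair it. Two-eye dependence becomes a further fault only if eyes are the unit. No primary or main secondary conclusion depends on this test. What is at risk is the interpretation of one supplementary P-value.

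**What to change.** In SAP section 3.2.2, item 12, delete the McNemar sentence, or keep the test and label it a descriptive summary of within-patient change that does not compare the drugs.

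If a dichotomized alternative is wanted, specify a logistic regression of final haze (above or below the cut) on treatment arm and baseline haze, with a patient random effect or GEE clustered on patient. State the cut-point for each grading scale and the visit that supplies the final value. The wording of the haze objectives in section 2.3.1 could be aligned to say that the change is compared between arms.

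The cost is SAP wording only. The haze data are already scheduled, and neither the sample size nor the main item 12 model changes. The replacement will have modest power (44% in the 40% versus 60% scenario above), so it should remain supplementary.

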2.3 Specific Aims

2.3.1 Specific Aim 1

Primary Objective. The primary objective of the study is **to establish which immunosuppressive treatment, methotrexate or mycophenolate mofetil, results in a higher rate of corticosteroid-sparing treatment success, on an intent to treat basis.** Specifically, we will compare the fraction of subjects who achieve treatment success at six months (as defined in the Manual of Operations Section 2.5.1) between the two groups.

Primary Outcome. The primary outcome for Specific Aim 1 will be the difference in the proportion of patients assigned to mycophenolate mofetil vs. methotrexate who achieve treatment success (as defined in the Manual of Operations Section 2.5.1).

Patients who experience success at 6 months with the drug to which they were originally randomized (in Specific Aim 1) will continue on the same drug for an additional 6 months. This will be called Phase I (6-12 months). Patients will then be seen every 3 months (and will be examined at 9 months and at 12 months), until success at 12 months or treatment failure at any time. Patients who fail treatment before 12 months with the initial drug will be removed from the study and treated according to best medical judgment.

Secondary Objectives

- To determine whether patients exhibit a difference in time to control of inflammation within the first six months.
- To determine whether patients exhibit a difference in time to corticosteroid sparing control of inflammation within the first six months.
- To evaluate the proportion of patients achieving treatment success at 5 months and sustaining, for at least 28 days, to 6 months.
- To evaluate a difference in control of inflammation in the posterior/pan anatomic locations only, assessed at by six months.
- To evaluate a difference in control of inflammation in the interior and anterior/intermediate anatomic locations only, assessed at by six months.
- To determine whether there is a change in best spectacle-corrected visual acuity at six months.
- To determine whether patients treated exhibit a difference in health related quality of life at six months.
- To determine if there are differences in discontinuing treatment due to each of the following reasons: safety, intolerability or lack of efficacy at six months.
- To determine whether patients exhibit a difference in the proportion of patients having macular edema at 6 months
- To determine whether patients exhibit a difference in macular thickness at 6 months

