The primary analysis is a logistic regression with treatment arm as a predictor. For the primary analysis, we propose to use study site as a *random effect* (random intercept model). The null hypothesis is that the regression coefficient for treatment arm equals zero, which will be tested using a likelihood ratio test with one degree of freedom. We will also fit the following models: (a) a model including drug, site, and drug \times site interaction, (b) a model including only drug and site, (c) a model including only drug and country, and (d) a model with drug, country, drug-country interaction, and site within country. Countries or sites with fewer than three observations will be pooled together. Provided there is no evidence of treatment \times site interaction or treatment \times country interaction, we will report pooled treatment effects and confidence intervals. In the event evidence suggests a difference between treatment sites, we will report treatment effects by site, and repeat the analysis excluding particular sites. Similarly, evidence of a treatment \times country interaction will lead us to report treatment effects and confidence intervals by country.

Simulations suggest that use of a model containing interaction terms between site or country and treatment for the primary analysis is undesirable. Such a procedure results in modest loss of power unless the treatment effect is of opposite sign in different sites or countries.

The hypothesis test is to be two-sided with alpha of 0.05. We propose to compute the P-value by permutation testing, based on the block randomization scheme.

Prespecified Subgroup Analysis.

The prespecified subgroup analysis will test the hypothesis that there is a treatment effect separately in each anatomic group, using a logistic regression model.

We denote the two anatomic groups by X_i^3 , which equals 0 when the patient is in the intermediate group and 1 when the patient is in the posterior/pan group. In the intermediate subgroup, we plan to determine whether there is evidence of a treatment effect (regardless of the effect in the posterior/pan group). Specifically, we will conduct this analysis in two ways: anatomical site at enrollment (split into three categories: anterior, anterior/intermediate or intermediate only, and posterior/panuveitis), and anatomical location by history (split into two

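### SAP 3.2.2 item 16: the non-inferiority rule is met automatically whenever the superiority test is not significant

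*Combined protocol and SAP*

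**What the plan says.** Item 16 of the planned secondary analyses in SAP 3.2.2 opens with a condition: "If no difference is found for the primary outcome comparing treatment success between arms". Only in that case is non-inferiority of methotrexate examined. The margin is set by the words "assuming a 10% non-inferiority margin" and is attributed to investigator consensus. Methotrexate is then to be declared "non-inferior to mycophenolate if the lower limit of the 95% CI for treatment success at 6 months is less than 10" percent. The item closes: "We are interested in a one-sided comparison given the cost differential between methotrexate and mycophenolate mofetil".

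The sentence does not say that the interval is for a between-arm difference, which arm is subtracted from which, or how the interval is obtained from the primary model, a logistic regression with a random site intercept.

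Three other places bear on it:

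- SAP 2.3.1 defines the primary outcome as "the difference in the proportion of patients assigned to mycophenolate mofetil vs. methotrexate who achieve treatment success".
- SAP 3.2.2, primary analysis: "The hypothesis test is to be two-sided with alpha of 0.05". SAP 3.4.1 adds that the final critical value shifts slightly because of the interim looks.
- SAP 11 records, under 13 January 2015, that a non-inferiority analysis was added. It does not restate the rule.

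No other section gives the rule in a correct form.

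**The concern.** A non-inferiority test has to rule out an unacceptable deficit. With a 10-point margin, the confidence limit on methotrexate's unfavourable side must exclude a 10-point loss. The written rule looks at a lower limit and asks whether it is below +10. That is a different question, and a non-significant superiority test has already answered it.

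The SAP justifies the analysis by cost: mycophenolate is much dearer, so a finding that methotrexate is not inferior would influence practice. As written, every inconclusive trial would produce that finding, with no control of the error rate. The analysis was added in January 2015, after enrollment began in August 2013 (protocol 2.2), so its credibility rests on the exact wording that was prespecified.

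**Working it through.** **Inputs.** Success rates 0.4 (methotrexate) and 0.6 (mycophenolate), 108 per arm, 10% loss by six months, two-sided alpha 0.05 and 80% power (SAP 3.4.1); margin 10 points (item 16). Evaluable patients: 108 × 0.9 = 97.2, taken as 97 per arm.

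**The plan's own figure.** Equation (5) in SAP 3.4.1 gives 2N = 4(1.960 + 0.842)² × 0.5 × 0.5 / 0.2² = 196.2. Multiplying by 1.1 gives 215.8 and dividing by 0.9 gives 218.0, so the stated 216 is reproduced. Power at 97 per arm is 80.0%. The SAP states no power for the non-inferiority claim.

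**The logic.** Let (L, U) be the 95% CI for methotrexate minus mycophenolate.

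- Item 16 runs only if the primary test is not significant, so L ≤ 0 ≤ U.
- Subtracting in this order, the lower limit is L ≤ 0 < +10 points. The rule is met.
- Subtracting in the other order, the CI is (-U, -L) and its lower limit is -U ≤ 0 < +10 points. The rule is met.

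**Does a mismatch between p-value and CI matter?** The primary p-value comes from a permutation test with an interim-adjusted critical value, so it need not agree exactly with the CI. Every possible 2×2 table with 97 per arm was enumerated. The interim-adjusted level, from the spending function in SAP 6.2.3 with looks at 1/3 and 2/3, is a nominal two-sided p of 0.048.

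| Primary test | Non-significant tables | Meeting the written rule | Largest lower limit |
|---|---|---|---|
| Likelihood ratio, 0.05 | 2068 | 2068 | +0.06 points |
| Fisher exact, 0.048 | 2280 | 2280 | +1.25 points |

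The result is the same in both subtraction orders and with 108 per arm.

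**An example.** Methotrexate 44/97 (45.4%), mycophenolate 57/97 (58.8%). The difference is -13/97 = -13.4 points. SE = √(0.454 × 0.546/97 + 0.588 × 0.412/97) = 0.0711, so the 95% CI is -13.4 ± 13.9, that is -27.3 to +0.5. The superiority test is not significant. The written rule declares non-inferiority although the interval reaches far beyond -10.

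**How often.** Exact binomial enumeration, 97 per arm, likelihood-ratio test at 0.05. The written rule is met exactly when the primary test is non-significant. The corrected rule requires L > -10 points.

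| True methotrexate / mycophenolate | Written rule | Corrected rule, all trials | Corrected rule and non-significant | Corrected rule, given non-significant |
|---|---|---|---|---|
| 0.60 / 0.60 | 95.1% | 30.5% | 28.0% | 29.4% |
| 0.50 / 0.60 | 70.8% | 2.8% | 2.8% | 3.9% |
| 0.40 / 0.60 | 19.3% | 0.04% | 0.04% | 0.2% |

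**Power of a correct rule.** At a common rate of 0.5, SE = √(2 × 0.5 × 0.5/97) = 0.0718 and the CI half-width is 1.96 × 0.0718 = 14.1 points, wider than the margin. Methotrexate would have to be observed about 14.1 - 10 = 4.1 points better to pass. Approximate power is Φ(0.10/0.0718 - 1.96) = 28.5%. For 80% power at equality, (1.960 + 0.842)² × 2p(1 - p)/0.10² gives 393 evaluable per arm at p = 0.5 and 377 at p = 0.4 or 0.6.

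**The case against.** The strongest reply is that this is a slip of wording around a recoverable intent. The item names the drug, the margin and a one-sided aim, and a competent analyst would probably apply the conventional rule. The 70.8% and 19.3% are simply the chances that superiority fails; they describe literal execution and not likely conduct. It is also one of 17 planned secondary analyses and leaves the primary test and sample size untouched. All of that is fair. It does not make the stated threshold valid, and two repairs that change different words (switch to the upper limit, or change the sign and the inequality) are both open to whoever runs the analysis.

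Second, the scale is not stated. If the interval were for methotrexate's success proportion alone, the rule would almost never be met at success rates of 0.4 or more (chance below one in a million) and would reward poor performance. If it were an odds ratio, a 10% limit would have no direct meaning. Automatic success is shown for a difference in proportions. That is the reading which SAP 2.3.1 and a margin against mycophenolate support, and the other readings do not rescue the rule.

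Third, the one-sided remark could mean a one-sided 5% bound. The corrected rule would then be met in about 41% of non-significant trials at equality. This stands as a reason to state the level. The SAP does specify a 95% CI, and a two-sided 95% CI corresponds to a one-sided 2.5% test.

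**Conclusion.** The rule is wrong as written and must be corrected. On the difference-in-proportions scale it is met in every trial in which it is run, in either subtraction order, so it carries no information beyond the non-significant primary test. It is not run at all if the primary test is significant. Read literally, the chance of a false non-inferiority claim is 70.8% at 50% vs 60%, where the intended one-sided level is 2.5%, and 19.3% at 40% vs 60%.

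These figures assume 97 evaluable patients per arm, an unadjusted comparison without the site effect and a test at 0.05. The logical result does not depend on the first two, and it survives the interim-adjusted level. The correction could change the trial's conclusion: even if the drugs are equal, a valid rule would be met in only about 28-31% of trials.

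**What to change.** Replace the decision sentence in item 16 with: *Methotrexate will be considered non-inferior if the lower limit of the two-sided 95% CI for the difference in 6-month treatment success (methotrexate minus mycophenolate) is greater than -10 percentage points.*

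In the same item:

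- say that this is a one-sided 2.5% test, which settles the one-sided remark against the statement in SAP 3.2.2 that all alpha levels are two-sided;
- name the method that yields the risk-difference CI, since the primary model is logistic;
- state that power is about 28-31% if the true rates are equal, so failing the test is not evidence that methotrexate is inferior.

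The core change is one sentence and the additions are a few lines. No patients, data or procedures change. The non-inferiority claim becomes harder to reach, as it should be.
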